## 3.7.2.1 Meal Challenge

Subjects will come into the clinic in a fasting state for Visit 2, with exception of treating hypoglycemia. Fasting will be defined as no intake of drink or food, with exception of water, for  $\geq$ 6 hours before the clinic visit. Subjects will also be instructed not to administer manual bolus doses of insulin during the 4 hours immediately preceding the meal challenge. If the subject requires a manual bolus insulin dose to correct hyperglycemia within the 4 hours prior to the scheduled visit, the meal challenge will need to be rescheduled.

The CGM glucose value will be confirmed 15 minutes before the start of the meal. If the subject's CGM value is  $\geq$ 70 mg/dL, the subject can start the meal challenge 15 minutes later. If the subject's CGM value is  $\leq$ 70 mg/dL, the Investigator can provide 15 g of fast-acting carbohydrates and reassess the CGM glucose value after 30 minutes and if the subject's new CGM value is  $\geq$ 70 mg/dL, the subject can start the meal challenge 15 minutes later. The CGM value obtained immediately before the start of the meal (defined as t=0) will serve as the baseline glucose value for that visit.

Subjects in the Afrezza groups will receive training on how to use the Afrezza Inhaler using BluHale technology, as well as how to identify and manage any events of hypo and hyperglycemia.

In addition to CGM, subjects will be instructed to take SMBG measurements 15 minutes before the start of the meal, immediately before the start of the meal (t=0), and at 15, 30, 45, 60, 90, and 120 minutes after the start of the meal challenge.

Confidential Page 45 of 70

mannkind

The meal challenge will consist of 1-2 bottles of Boost nutritional shake (1 bottle is approximately 240 calories, 41 g carbohydrate, 10 g protein, and 4 g fat). The meal is to be fully consumed within 15 minutes. Each Afrezza dose will be administered at the start of the meal challenge. The RAA dose will be administered  $10 \pm 5$  minutes (per label) before the start of the meal challenge, per Investigator discretion.

For Afrezza doses exceeding 12 units, inhalations from multiple cartridges are necessary. To achieve the required total mealtime dose, subjects should use a combination of 4-unit, 8-unit, and 12-unit cartridges.

The blood glucose monitoring values and CGM values (if available) will be entered in the CRF completed at Visit 2. Afrezza subjects will remain under clinical supervision for the 2 hours after their dose of Afrezza. Subjects should have glucagon available for use in the event of hypoglycemia and should not be discharged until hypoglycemia is resolved.

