- e. Subjects will be asked to provide a recent negative COVID-19 test (if available), confirm they have no symptoms of COVID-19, or provide evidence of COVID-19 vaccination.
- f. Subjects should use their study provided blood glucose meter to take an SMBG value if their CGM reading is <70 mg/dL or if their CGM reading does not match their symptoms or expectations. Hypoglycemic episodes will be defined as all SMBG measurements <70 mg/dL. See Section 3.9.2.6.
- g. A negative urine pregnancy test is required for enrollment, from all female subjects of child-bearing potential. After enrollment, additional pregnancy tests may be conducted as needed at the discretion of the Investigator.
- h. A documented normal level within 6 months of screening can be used in lieu of testing.
- i. CGM reports and pump reports will be downloaded from V1 to V2 at V2, V2 to V9 and 10 days before V9 to V9 at V9, V9 to 30 days after V9 at V13, and 30 days before V14 to V14 and V13 to V14 at V14 using Carelink for Medtronic CGM and pumps. CGM reports/data and pump reports/data will be downloaded from V1 to V2 at V2, V2 to V9 and 10 days before V9 to V9 at V9, V9 to 30 days after V9 at V13, and 30 days before V14 to V14 and V13 to V14 at V14 using Clarity for Dexcom CGM and t:connect for Tandem pumps. The site will de-identify all reports and data.
- j. Subjects in the Afrezza + AID group will be instructed not to enter carb intake/meal announcements in the pump system. In the event that they accidentally enter carb intake/meal announcement for a certain meal, they should NOT dose Afrezza for that same meal. If they accidentally take Afrezza with a meal announcement, carbs or glucagon should be administered. For subjects in the Afrezza + AID group, the site will confirm at every visit (phone or in person) to make sure they are not entering carb intake/meal announcements in the pump system.
- k. Only applies to subjects in the Afrezza + Insulin Degludec group who use a Medtronic 670G/770G system.

Confidential Page 40 of 70

Table 4: CGM/Pump Reports and Data to be Downloaded

| Reports/Data to be Downloaded                 | V2 | V9 | V13 | V14 |
|---|----|----|-----|-----|
| Blinded G6 PRO Data                           | X  |    |     | X   |
| V1 to V2 CGM/pump report/data                 | X  |    |     |     |
| V2 to V9 CGM/pump report/data                 |    | X  |     |     |
| V9 minus 10 Days to V9 CGM/pump report/data   |    | X  |     |     |

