## 3.7.2 Randomization (V2)

When subjects return for Visit 2, blinded CGM data will be downloaded and CGM sensor wear evaluated. If CGM sensor wear time is inadequate, per the discretion of the Investigator, the Screening Period can be extended and sensor wear can be repeated once (this becomes an unscheduled visit). The subject will return to the clinic 10 days (+4 days) later and, if sensor wear is adequate and all eligibility criteria met, be randomized to study treatment and proceed with the meal challenge and Visit 2 assessments. Visit 2 should be within 4 days of the end of the final sensor wear data (i.e., the CGM sensor with adequate wear time).

The following procedures will be performed at Visit 2:

- Enrollment (if eligibility criteria are met)
- Record concomitant medications
- Record current basal insulin dosages
- Remove blinded Dexcom G6 Pro CGM

Download and de-identify data from Dexcom G6 Pro device (

Confidential Page 42 of 70

• )

mannkind

Download and de-identify of unblinded CGM reports and pump reports for Medtronic CGM and pumps (

Confidential Page 43 of 70

mannkind

Download and de-identify of unblinded CGM reports/data and pump reports/data for Dexcom CGM and t:connect for Tandem pumps (

Confidential Page 44 of 70

- )
- Subjects randomized to study treatment (Afrezza + Insulin Degludec, Afrezza + AID, or AID Control)
- Disbursement/placement of unblinded CGM sensor (only applies to subjects in the Afrezza + Insulin Degludec group who use a Medtronic 670G/770G system)
- Conduct 2-hour, in-clinic meal tolerance test
- Subjects will take their first dose of Afrezza or their dose of RAA with standardized meal challenge as described in Section 3.7.2.1.
- Record AEs
- Record any hypoglycemic episodes (see Section 3.9.2.6)
- Provide additional subject training, as needed, on CGM use, including but not limited to the
  use of alerts, interpretation of trends, interfering substances, and contraindications.

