### 3.9.2.6 Hypoglycemic Events

A hypoglycemic episode is defined as any event with SMBG <70 mg/dL (i.e., Level 1 hypoglycemia) or SMBG <54 mg/dL (i.e., Level 2 hypoglycemia) (ADA 2021a) on the study-provided glucose meter. Severe hypoglycemic events are defined as events requiring assistance of another person to actively administer carbohydrate, glucagon, or other resuscitative actions. Severe hypoglycemic events will be documented as SAEs in the CRF. Nonsevere hypoglycemic events will not be documented as AEs but will be recorded in the hypoglycemia page of the CRF.

After the standardized meal challenge at Visit 2, subjects will be monitored for signs of hypoglycemia. Subjects exhibiting signs of hypoglycemia will be treated as appropriate (e.g., provided with a snack or glucose). The type of treatment given and time will be recorded and subjects will remain in-clinic until hypoglycemia is resolved.

In the event that the subject accidentally enters carb intake/meal announcement for a certain meal and also doses with Afrezza, carbohydrates or glucagon should be administered. The subject should be instructed to contact the Investigator and site staff as soon as possible following the event to ensure prompt review and to give the Investigator the opportunity to address any further necessary measures for correction.

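### The meal challenge and first double-dose Afrezza inhalation can start on one CGM value 15 minutes old; the meter readings at -15 min and t=0 carry no hold rule

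*Protocol*

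**What the plan says.** Protocol Section 3.7.2.1 sets the start condition on CGM alone: "The CGM glucose value will be confirmed 15 minutes before the start of the meal". If that value is at least 70 mg/dL, the challenge can begin 15 minutes later. If it is low, the Investigator can give 15 g of fast-acting carbohydrate, look at CGM again after 30 minutes and, if it is then at least 70, start 15 minutes after that. The t=0 CGM value serves as the visit baseline and has no threshold.

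The same section also schedules meter readings: "subjects will be instructed to take SMBG measurements 15 minutes before the start of the meal, immediately before the start of the meal (t=0"), and then from 15 to 120 minutes. No threshold or action is attached to the two pre-meal readings. What is said about them is that they are recorded: "The blood glucose monitoring values and CGM values (if available) will be entered in the CRF completed at Visit 2".

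On dosing and eating: "Each Afrezza dose will be administered at the start of the meal challenge", and "The meal is to be fully consumed within 15 minutes". Section 3.4.4 sets the first dose at twice the calculated RAA dose, rounded down to a 4-unit step and capped at 24 units.

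Hypoglycemia is a meter-based concept throughout. Table 3, footnote f: "Hypoglycemic episodes will be defined as all SMBG measurements <70 mg/dL". Section 3.9.2.6 agrees: "A hypoglycemic episode is defined as any event with SMBG <70 mg/dL". The Visit 2 procedure list in Section 3.7.2 calls for these to be captured: "Record any hypoglycemic episodes (see Section 3.9.2.6").

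**The concern.** The start check exists to avoid giving a first, deliberately high dose to someone who is already low. As written it uses a reading that is 15 minutes old when Afrezza is inhaled, from the device the protocol does not use to define hypoglycemia. Two readings from the device that does define it are in hand before inhalation and change nothing on paper.

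The dose matters here. Section 1.2 describes the conversion ratio as well above the label's. Section 1.1 puts peak insulin about 12 to 15 minutes after inhalation, while the meal may take up to 15 minutes to drink. Section 1.3.1 lists severe hypoglycemia as an important identified risk. What is at stake is a small in-clinic safety exposure at Visit 2. The HbA1c and CGM outcomes are not at stake.

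**Working it through.** There is no stated figure to reproduce; Section 5.6 says the 25 was not derived statistically. The check has two parts.

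**1. What each pre-dose reading does (Section 3.7.2.1).**

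| Reading | Time | Written effect on start |
|---|---|---|
| CGM | -15 min | Start permitted if at least 70 mg/dL |
| SMBG | -15 min | None |
| CGM | t=0 | None (baseline value) |
| SMBG | t=0 | None |

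One of four readings governs the start. The low-CGM branch is the same in kind: one repeat CGM value, again 15 minutes before the meal, so the earliest start is 30 + 15 = 45 minutes after the low reading. A subject at exactly 70 mg/dL at the check would reach the Level 2 threshold of 54 by t=0 with a fall of (70 - 54)/15 = 1.07 mg/dL per minute, and any fall at all would put the subject below 70. No written step at t=0 would stop the dose.

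**2. How often it might happen.** The documents give no device accuracy, fasting glucose distribution or short-term drift, so every input below is an assumption:

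- fasting glucose G lognormal, (mean, SD) = (120, 35), (120, 40), (130, 37.5), (140, 35), (140, 40) mg/dL
- CGM = G × (1 + e·Z), with e = 0.08, 0.10 or 0.15
- SMBG = G × (1 + 0.05·Z), with independent errors
- glucose at t=0 = G + d·Z, with d = 5, 10 or 15 mg/dL

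Here Z is standard normal. With 2,000,000 draws per setting, and all probabilities joint with CGM at -15 min of at least 70:

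| Event | Lowest | Mid-range (130, 37.5; e = 0.10; d = 10) | Highest |
|---|---|---|---|
| SMBG < 70 at -15 min | 0.15% | 0.6% | 1.8% |
| SMBG < 70 at t=0 | 0.27% | 1.7% | 5.0% |
| SMBG < 54 at t=0 | | | 1.0% |

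In subjects, using the unrounded 0.265% and 4.95% at t=0:

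- t=0, 20 Afrezza subjects: 20 × 0.00265 = 0.05 to 20 × 0.0495 = 0.99 expected. Chance of at least one: 1 - (1 - 0.00265)^20 = 5% to 1 - (1 - 0.0495)^20 = 64%.
- Mid-range at t=0: 20 × 0.017 = 0.34 expected.
- -15 min, all 25: 25 × 0.00148 = 0.04 to 25 × 0.0178 = 0.45 expected.

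The values are mostly shallow: across settings the median SMBG among affected subjects is 66 to 68 at -15 min and 62 to 67 at t=0. SMBG below 54 at -15 min is at most 0.02%.

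The top of the t=0 range depends on drift SD 15 mg/dL over 15 minutes. With the same glucose inputs (120, 40) and drift SD 5, the t=0 figure is 1.9% to 2.2%.

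**The case against.** The strongest reply is that existing text already covers this. The start wording permits and does not oblige. Section 1.2 leaves the initial dose to Investigator discretion, and it is given under supervision. Section 3.9.1.2 has subjects use the meter for treatment decisions when CGM does not match symptoms or expectations, and a meter value below 70 beside a passing CGM is arguably such a mismatch. The word confirmed in the start rule might mean confirmed by the meter reading taken at the same time. After dosing, the subject drinks 41 to 82 g of carbohydrate against the 15 g the protocol uses to treat a low, is watched for 2 hours with repeated meter readings, and has glucagon at hand.

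Most of this stands as mitigation, and it is why the point is minor. It does not supply a hold rule. The discretion concerns the dose in general. A passing CGM without symptoms does not itself trigger the meter check in Section 3.9.1.2 or Section 1.3.3. The sentences after the word confirmed refer only to the CGM value. The meal, supervision and glucagon act after the dose and do not bear on whether to give it.

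A missing CGM value is a weaker part of the point. The remark about availability concerns CRF entry, and subjects keep wearing their own CGM. A fallback is worth a clause, no more.

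A reader might infer that the protocol directs staff to dose a hypoglycemic subject, or that pre-dose glucose goes unmonitored. The documents support neither. Readings are taken, staff are free to hold, and the gap is only that no text tells them to.

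**Conclusion.** The point holds as a small safety clarification. The written start condition rests on one CGM value 15 minutes before inhalation, and a subject with an SMBG below 70 mg/dL at -15 min or t=0 meets it. That much follows from the text alone.

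The size rests wholly on assumed inputs and shows only that the event is uncommon. Even at the highest setting, with 0.99 expected of 20, a Poisson approximation gives e^-0.99 × (1 + 0.99) = 74% for none or one. Nothing in the planned HbA1c or blinded CGM summaries changes. It is an optional improvement, justified because the readings it needs are already scheduled.

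**What to change.** Keep the CGM rule in Section 3.7.2.1 and add one paragraph, for example:

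> Do not give the RAA bolus if the -15 min SMBG is <70 mg/dL, and do not give Afrezza if the -15 min or t=0 SMBG is <70 mg/dL, even if CGM is ≥70 mg/dL; use SMBG alone if CGM is unavailable. Give 15 g fast-acting carbohydrate, recheck after 30 minutes, and start once SMBG is ≥70 mg/dL, repeating the same day as needed. Rescheduling is at the Investigator's discretion, and Day 0 remains the day of randomization. In AID Control, if SMBG is <70 mg/dL at t=0 after the bolus, start the meal at once.

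AID Control needs its own line because the RAA bolus goes in 5 to 15 minutes before the meal, so a t=0 reading comes too late to hold it.

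Cost: on the assumptions above, 0.35% to about 5.7% of subjects in the Afrezza groups would pass today but be held (SMBG below 70 at either time), against 0.15% to 1.8% in AID Control. Expected number held = 20 × P(either) + 5 × P(-15 min): 20 × 0.0035 + 5 × 0.0015 = 0.08, up to 20 × 0.0566 + 5 × 0.018 = 1.2 of 25. Each is delayed by roughly 30 to 45 minutes or more, and pre-meal carbohydrate affects that subject's meal-test baseline.

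A stricter gate, requiring both devices to pass and rescheduling any failed recheck, is not worth it. It would also bind subjects with a low -15 min CGM. Expected reschedules would reach about 0.63 of 20 Afrezza subjects if 15 g carbohydrate raises glucose by 30 mg/dL on average, and about 1.4 with a 15 mg/dL rise. The rises are assumed, and both figures are upper bounds because some of these subjects already fail the current recheck. Rescheduling would fall after randomization, while later visits are timed from Visit 2.

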## 3.7.3 Telephone Visits (T3-T8)

- Telephone Visits 3 to 8 will be conducted as summarized below:
  - T3 phone call on Day 1 (the day after randomization on Day 0)
  - T4 phone call on Day 2
  - T5 phone call on Day 4
  - o T6 phone call on Day 7 ( $\pm$  2 days)
  - $\circ$  T7 phone call on Day 14 ( $\pm$  2 days)
  - o T8 phone call on Day 21 ( $\pm$  2 days)

### At these visits:

- Record changes to concomitant medications
- Record any AEs
- Record hypoglycemic events
- Titrate mealtime, correction and basal insulin dosages
- Answer subjects' questions/concerns
- Remind subjects in the Afrezza + AID group to NOT enter carb intake/meal announcements into their insulin pump during the study, to avoid the risk of an automated insulin bolus (i.e., to avoid stacking insulin).

### 3.7.4 Clinic Visit (V9)

- Record changes to concomitant medications
- Record any AEs
- Record hypoglycemic events
- Collect and review glucose meter data

Download and de-identify of unblinded CGM reports and pump reports for Medtronic CGM and pumps (

Confidential Page 46 of 70

• )

mannkind

Download and de-identify of unblinded CGM reports/data and pump reports/data for Dexcom CGM and t:connect for Tandem pumps (

Confidential Page 47 of 70

- )
- Remind subjects in the Afrezza + AID group to NOT enter carb intake/meal announcements into their insulin pump during the study, to avoid the risk of an automated insulin bolus (i.e., to avoid stacking insulin).
- Titrate mealtime, correction and basal insulin dosages
- Record current basal insulin dosages
- Assess the need for Afrezza correction dosing based on CGM profile (Afrezza groups only)
- Provide subject with any needed supplies (e.g., glucose test strips, Afrezza cartridges)

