#### 2 STUDY OBJECTIVES

#### 2.1 Primary Objective

The primary objective of this study is:

- To evaluate the change in HbA1c from baseline to end of study in adults ≥18 years of age with T1DM for each of the three following groups:
  - Afrezza + AID: Afrezza for bolus (mealtime) in combination with use of a CSII pump with an AID algorithm using a RAA for basal and correction insulin coverage
  - Afrezza + Insulin Degludec: Afrezza for bolus (mealtime and correction) in combination with insulin degludec for basal insulin coverage
  - AID Control: CSII pump with an AID algorithm using an RAA for all bolus (mealtime and correction) and basal insulin coverage

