#### 3 INVESTIGATIONAL PLAN

#### 3.1 Overall Study Design and Plan

[figure not shown]
MKC-TI-192 is a Phase 4, 90-day, randomized, three-arm, multicenter clinical trial evaluating the treatment paradigm and efficacy of Afrezza in controlling postprandial glucose in adult subjects (≥18 years of age) with T1DM. Subjects will be randomized to one of three treatment groups (two Afrezza groups and one control group):

- Afrezza + AID: Subjects in this group will use Afrezza for their bolus (mealtime) insulin and a CSII pump with an AID algorithm using RAA for their basal and correction insulin coverage.
- Afrezza + Insulin Degludec: Subjects in this group will use Afrezza for their bolus (mealtime and correction) insulin and insulin degludec for basal insulin coverage.
- AID Control: Subjects in this group will use a CSII pump with an AID algorithm using RAA for all bolus (mealtime and correction) and basal insulin coverage (control group).

See Figure 1 for a schematic of the study design.

Confidential Page 22 of 70

Figure 1: MKC-TI-192 Study Schematic

 $AID = automated insulin delivery, CGM = continuous glucose monitor, CSII = continuous subcutaneous insulin infusion, FEV_1 = forced expiratory volume in 1 second, HbA1c = glycated hemoglobin A1c, T1DM = type 1 diabetes mellitus$ 

- a. The Screening Visit should be scheduled 10 days (+ 4 days) before the subject's expected date of randomization. Subjects will be provided with a blinded Dexcom G6 Professional CGM device at the Screening Visit, which they will use in addition to their own CGM device during the Screening Period. At Visit 2, blinded CGM data will be downloaded and CGM sensor wear evaluated. If CGM sensor wear time is inadequate, per the discretion of the Investigator, the Screening Period can be extended and sensor wear can be repeated once. The subject will return to the clinic 10 days (+ 4 days) later and, if sensor wear is adequate and all eligibility criteria met, be randomized to study treatment and proceed with the meal challenge.
- b. Only applies to subjects in the Afrezza + Insulin Degludec group who use a Medtronic 670G/770G system.

Confidential Page 23 of 70

The study is composed of up to 5 clinic visits (screening, 3 treatment visits, and an end-of-treatment visit) and 9 telephone visits:

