#### 3.4.4 Dosage Schedule

Subjects in the Afrezza groups (Afrezza + Insulin Degludec and Afrezza + AID) will administer their first dose of Afrezza at Visit 2, at the start of the meal challenge. Afrezza will be dosed at 2 × the calculated RAA dose rounded down to the nearest 4-unit dose (based on their I:CHO dose calculated for mealtime), but not exceeding 24 units of Afrezza. The Afrezza dose will be administered at the start of the meal challenge. The start of the meal will define t=0. After the

Confidential Page 31 of 70

meal challenge and at subsequent visits, Afrezza will be titrated to glycemic effect per Investigator discretion.

Table 2: Starting Dose of Afrezza for Subjects in the Afrezza Groups

| RAA Dose (Units) | Afrezza Dose (Units) |
|------------------|----------------------|
| <4               | 4                    |
| 4                | 8                    |
| 5                |                      |
| 6                | 12                   |
| 7                |                      |
| 8                | 16                   |
| 9                |                      |
| 10               | 20                   |
| 11               |                      |
| ≥12              | 24*                  |

RAA=rapid-acting insulin analog (e.g., insulin aspart or insulin lispro)

Note: Aside from the initial mealtime dose cap mentioned (24 units of Afrezza), there is no maximum dose of Afrezza and the required total mealtime dose for the subject during the study may differ from the examples provided in this table.

Following the initial dose of Afrezza and throughout the study, post-meal insulin correction doses can be taken no sooner than 60 to 90 minutes after a previous dose of Afrezza if the subject's glucose value is >160mg/dL, or per investigator discretion. Subjects in the Afrezza+AID group will correction dose with RAA while subjects in the Afrezza+Tresiba group will correction dose with Afrezza.

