|  | Afrezza Groups Only            |    |                  |    |    |    |    |    |    |      |                 |      |     |             |      |
| Training for use and storage of Afrezza  |                                | X  |                  |    |    |    |    |    |    |      |                 |      |     |             |      |
| Training, as needed, on CGM use including but not limited to the use of alerts, interpretation of trends, interfering substances, contraindications, etc |                                | X  | X                | X  | X  | X  | X  | X  | X  | X    | X               | X    | X   |             |      |
| Dispense Afrezza
inhalers and
cartridges, as
necessary  |                                | X  |                  |    |    |    |    |    | X  |      |                 |      | X   |             |      |

Page 38 of 70

| Study Period   | Screen                      |    | Treatment Period |    |    |    |    |    |    |      |                 |      |     |             |      |
|--|-----------------------------|----|------------------|----|----|----|----|----|----|------|-----------------|------|-----|-------------|------|
| In-clinic Visit (V) Telehealth Visit (T)   | V1                          | V2 | Т3               | T4 | Т5 | Т6 | Т7 | Т8 | V9 | T10  | T11             | T12  | V13 | V14         | ET c |
| Day  | Up to 28 Days               | 0  | 1                | 2  | 4  | 7  | 14 | 21 | 30 | 37 b | 44 b | 51 b | 80  | 90
(EOT) |      |
| Visit Window (Days)  | Before Random. a |    |                  |    |    | ±2 | ±2 | ±2 | +7 | ±2   | ±2              | ±2   | +2  | +7          |      |
| Disbursement/ placement of unblinded CGM sensors k   |                             | X  |                  |    |    |    |    |    | X  |      |                 |      |     |             |      |
| Training on use of unblinded CGM k  |                             | X  |                  |    |    |    |    |    |    |      |                 |      |     |             |      |
| Assess the need for
Afrezza correction
dosing based on CGM
profile  |                             |    | X                | X  | X  | X  | X  | X  | X  |      |                 |      |     |             |      |

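### Table 3 and Protocol 3.7.4 prompt sites to assess Afrezza correction dosing in both Afrezza groups, while the arm definitions and 3.4.4 assign RAA correction to Afrezza + AID

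*Protocol*

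**What the plan says.** The primary objective (Protocol 2.1) describes Afrezza + AID as Afrezza at meals together with a pump "using a RAA for basal and correction insulin coverage". The design section (3.1) agrees: this arm has "a CSII pump with an AID algorithm using RAA for their basal and correction insulin coverage". For the other Afrezza arm, 3.1 says: "Subjects in this group will use Afrezza for their bolus (mealtime and correction) insulin and insulin degludec for basal insulin coverage". SAP 8.1 repeats both definitions.

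Protocol 3.4.4 states the rule for correction doses arm by arm: "Subjects in the Afrezza+AID group will correction dose with RAA while subjects in the Afrezza+Tresiba group will correction dose with Afrezza". Tresiba is the insulin degludec product (section 1.3.2).

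The visit instructions read differently. The V9 list in 3.7.4 contains the item "Assess the need for Afrezza correction dosing based on CGM profile (Afrezza groups only". Table 3 has a row "Assess the need for Afrezza correction dosing based on CGM profile" in the block headed "Afrezza Groups Only", marked at T3, T4, T5, T6, T7, T8 and V9. Neither place limits the task to one of the two Afrezza arms.

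**The concern.** Two features separate the Afrezza regimens: how basal insulin is delivered, and which insulin is used for correction. The text that defines the arms settles the second feature. The schedule and the V9 checklist, which staff have in hand at each contact, ask a question in Afrezza + AID that the arm definition has already answered.

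The primary objective is to describe the HbA1c change for each group as defined, with hypoglycemia as a secondary objective. If sites read the prompt as permission, some Afrezza + AID subjects could receive corrections outside their stated regimen. That arm's summaries would then be a less clean description of it. Section 5.13 also plans summaries of bolus doses by visit, and their meaning depends on which insulin is used for what.

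**Working it through.** This is a check of text against text. No sample size, power or variance enters, and section 5.6 says that the 25 subjects were not derived statistically.

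**1. Which arms are the Afrezza groups?** Section 3.4.4 spells it out: "Subjects in the Afrezza groups (Afrezza + Insulin Degludec and Afrezza + AID) will administer their first dose of Afrezza at Visit 2". Section 3.4.3 uses the term in the same way. It covers both arms.

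**2. Could the Table 3 row be meant for the degludec arm alone?** Other rows in the same block are restricted where that was intended. Dispensing degludec and recording basal dosages are each labelled for the degludec group only. The unblinded CGM rows carry footnote k, which limits them to degludec-arm subjects on a Medtronic system. The correction row has neither a label nor a footnote.

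**3. Does 3.4.4 leave an exception?** Its mention of investigator discretion belongs to the sentence on the timing of post-meal corrections and the glucose threshold. The next sentence, which names the insulin for each arm, has no exception.

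**4. The passages side by side.**

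| Place | Afrezza + AID | Afrezza + Insulin Degludec |
|---|---|---|
| Protocol 2.1, 3.1; SAP 8.1 | RAA for correction | Afrezza for correction |
| Protocol 3.4.4 | RAA for correction | Afrezza for correction |
| Protocol 3.7.4 (V9) | assess need for Afrezza correction | assess need for Afrezza correction |
| Table 3 (T3-T8, V9) | assess need for Afrezza correction | assess need for Afrezza correction |
| Protocol 3.7.3 (T3-T8) | no such item | no such item |

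The degludec column is consistent apart from the missing item in 3.7.3. The Afrezza + AID column is not.

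**5. Coverage.** As written, the prompt applies to 10 + 10 = 20 of the 25 planned subjects. The arm definitions give Afrezza correction to 10 of them. The difference, 20 - 10 = 10, is the planned Afrezza + AID arm. This counts whom the wording covers. It does not count departures.

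**6. Table 3 against the visit lists.** Table 3 marks 6 telephone contacts and 1 clinic visit, so 7 in all. Section 3.7.4 carries the item for the clinic visit. Section 3.7.3, for the 6 telephone contacts, lists only a general titration of mealtime, correction and basal insulin. At those contacts the prompt rests on Table 3 alone, although section 3.7 tells sites to perform procedures as Table 3 indicates.

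**7. Would departures be visible afterwards?** Table 3 marks an instruction on logging at V2 and V13, but it schedules collection of Afrezza dose information only at V14. Sections 3.1, 3.7.6 and 3.7.7 describe that log as covering the final 10 days. With V14 at Day 90 (+7), the log starts at about Day 90 - 10 = 80. The prompts run from Day 1 (T3) to Day 30 (+7) (V9), so the two periods do not overlap.

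**The case against.** The strongest reply is that assessing a need is not giving a dose. No sentence in either document tells an Afrezza + AID subject to correct with Afrezza. A site can review the CGM profile in both arms, apply 3.4.4 in each, and regard the item as not applicable in Afrezza + AID. This stands, and it limits the point: a departure is possible, not instructed. But nothing tells sites to treat the item that way.

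A second reply is that the phrase may be shorthand for any correction given after an Afrezza meal dose, since 3.4.4 frames corrections in both arms by the time since the last Afrezza dose. That reading is available but not the literal one, and the literal text is what conflicts.

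A third reply is that the study is descriptive, its primary efficacy population is ITT, and section 5.8 already provides for review of all deviations before lock. This too has weight. An occasional off-regimen correction would not undo an ITT summary, so a reader should not conclude that the results would cease to describe the regimen. Deviation review gives less comfort than it seems to, because the Afrezza dose log does not reach back to the contacts in question. For the same reason, flagging contrary doses in the exposure listing would not be a workable remedy on the data as scheduled.

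**Conclusion.** The inconsistency is real and should be corrected. It concerns one arm of 10 planned subjects and a feature that distinguishes it from the other Afrezza arm. There is a secondary mismatch between Table 3 and section 3.7.3. The effect on HbA1c or hypoglycemia cannot be sized from the documents.

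Two stronger readings are tempting, and neither is supported. A reader might multiply subjects by contacts, or note that each subject is 1/10 of the arm, and take the result as the extent of the damage. Those figures count marks on a schedule and say nothing about how many subjects would depart from 3.4.4. A reader might also infer that the prompt creates the insulin stacking that the protocol warns against. Those warnings (3.7.2 to 3.7.4) concern meal announcements that trigger an automated pump bolus, not the choice of correction insulin, and they cannot be carried over.

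The conclusion assumes that the term for the Afrezza groups keeps its 3.4.3 and 3.4.4 meaning throughout, and that the Table 3 block heading governs the row, which falls on the following page of the table. The wording of 3.7.4 itself supports the second assumption.

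**What to change.** Reconcile the Table 3 row, section 3.7.3 and section 3.7.4 with sections 2.1, 3.1 and 3.4.4 and with SAP 8.1, so that every place names the same correction insulin for each arm. Which rule applies is for the sponsor to decide. In the same edit, make Table 3 and 3.7.3 agree on whether the assessment takes place at T3 to T8.

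If the arm definitions stand, the change is to one table row, one bullet in 3.7.4 and the T3-T8 list. If the sponsor decides otherwise, the synopsis, the primary objective, the design section, 3.4.4 and SAP 8.1 all need amendment. That would redefine an arm and would no longer be an editorial correction. Neither route calls for a change to the sample size or the planned summaries.
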